47 48 Standard treatment for Sever's disease is placement of heel cups in shoes and stretching or 49 physical therapy. These interventions are effective in reducing Sever's patients' heel pain.¹²⁻¹⁶ A 50 retrospective study showed that with treatment with a heel cup or other foot orthoses, symptoms improved within 2 months.⁸ However, there remains a distinct lack of randomized control trials 51 evaluating treatments for Sever's in the literature.¹⁷ For the many young athletes with Sever's who 52 53 participate in barefoot sports such as gymnastics, dance, or tae kwan do, the standard treatment is 54 inadequate. They cannot use the recommended heel cups, which are placed in an athletic shoe. 55 Currently, two braces are commonly used for barefoot athletes with Sever's: Cheetah Heel Cups 56 and The X Brace. Neither of these braces are currently FDA approved as they are not considered 57 medical devices and are marketed as an insert. Health care providers often recommend barefoot 58 athletes purchase these braces, but no published studies evaluating their effectiveness exist in the 59 established literature. This study will compare these two braces in an investigator-blinded, 60 randomized control trial in order to contribute to the understanding of standard treatment for 61 barefoot athletes with Sever's disease and improve patient outcomes by affecting clinical practice. 62 In light of the paucity of information on and the importance of optimizing patient outcomes to 63 improve quality of life and maintain an active lifestyle for young barefoot athletes, this prospective, 64 randomized treatment study will compare the effectiveness of two braces in decreasing pain 65 severity in barefoot athletes diagnosed with Sever's disease. 66 67 III. Preliminary Studies/Progress Report: 68 No preliminary studies have been conducted at this institution. 69 70 IV. Research Methods 71 A. Outcome Measures: 72 i. Primary Outcome: Oxford Ankle Foot Questionnaire for Children (OxAFQ-C) Scores 73 ii. Visual Analog Scale (VAS) Pain Score 74 iii. Subject-Reported Compliance with Brace Use 75 1. Hours per week the brace was worn with barefoot sport activity 76 iv. **Rest from Sport** 77 1. Amount of time per week taken off from barefoot sport due to pain (if 78 applicable) 79 Acceptability of Brace ν. 80 1. Comfort (Comfortable: Y/N) 81 2. Appearance (Acceptability: Y/N) 82 3. Perceived Effect on Athletic Performance (Improvement: Y/N) 83 Pain Medicine Usage vi. 84 1. Weekly dosage of pain medicine (if applicable) 85 B. Explanatory Variables: 86 i. Demographic 87 1. Name and Medical Record Number 88 2. Date of Birth 89 3. Age at time of visit

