
90		4. Gender
91		5. Ethnicity
92		6. Weight
93		7. Height
94		8. BMI
95		9. Athletic participation
96		10. Primary sport
97		11. Hours per week in a barefoot sport
98		ii. History
99		1. Previous diagnosis of Sever's or calcaneal apophysitis
100		a. Brace previously used
101		
102		
103		4
104		
105		
106		
107		
108		
109		
110		
111		
112		
113		
114		
115		Figure 1. Cheetah Brace Figure 2. The X Brace
116		
117	C.	Description of Population to be Enrolled:
118		Barefoot athletes who present to sports medicine clinic for foot, ankle, or heel pain.
119		i. Inclusion Criteria:
120		1. Aged 7-14 years
121		2. Participate in barefoot sports including: martial arts, dance, gymnastics, or
122		acrobatics
123		3. A clinical diagnosis of Sever's or calcaneal apophysitis
124		ii. Exclusion Criteria:
125		1. History of foot/ankle surgery
126		2. History of rheumatologic diagnoses
127		3. Prisoners, pregnant females, individuals with limited decision-making capacity
128		
129	D.	Study Design and Research Methods
130		i. Human Subject Considerations
131		1. All patients will have an established relationship with a Children's Hospital
132		Sports Medicine Physician.
133		2. All PHI will be stored within REDCap.
134		ii. Study Design: Randomized Treatment Study
135		iii. Methods:

136	1. Subjects will be recruited face-to-face by a study team member at time of initial
137	visit, diagnostic clinical visit, or phone call initiated by [name]. Subjects
138	recruited via phone call will be patients of study personnel. Patients and
139	families interested in participating in the study will be contacted by a member
140	of the study team to set up a research only consent visit. If they cannot come
141	into clinic, the informed consent and assent will be sent to the family and a
142	research assistant with call the family, either via phone or video call, to go over
143	the consent and assent in real time and to answer any questions. After a signed
144	consent or assent form is received by the research assistant, the assigned brace
145	will be sent in the mail to the family and the associated questionnaires will be
146	sent via email.
147	2. Subject will be screened for inclusion/exclusion (enrollment) criteria by study
148	team member through chart review.
149	3. If subject meets enrollment criteria, they and a legal guardian will be consented
150	face-to-face by a study team member.
151	a. Consent will be sought from subjects ages 13-14.

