152	b. Assent will be sought from athletes younger than 13 years of age.
153	c. Consent will be sought from parents of subjects ages 7-14.
154	4. [name] or designated staff will answer any questions after the patient and
155	his or her parents have read and reviewed the informed consent and assent
156	forms. It will be emphasized to the patients that their decision to participate in
157	the study will in no way impact their treatment. Comprehension will be
158	assessed by reviewing the consent forms with the patient and his or her parents
159	thoroughly and asking the subjects questions requiring more than a simple
160	yes/no answer.
161	a. Patients and parents will sign the appropriate line on the informed
162	consent/assent form.
163	b. Consent procedures will take place in a private room or over a private
164	call.
165	5. Subject will complete initial demographics survey, OxAFQ-C, and VAS.
166	6. Subject will be randomized into either the Cheetah Heel Cup or The X Brace
167	treatment group. The randomization scheme will be independently created by
168	the research assistant. The random assignment will be kept blind to the PI and
169	statistician.
170	7. Subject will receive their assigned brace in the mail following their consent visit.
171	Subjects will receive an activity and rest log in the mail with their
172	brace. This is a weekly log and will help subjects track their weekly
173	activity in their barefoot sport (in hours), amount of time spent in
174	brace during barefoot sport (in hours), and any rest time taken from
175	their barefoot sport (in hours). This log is optional, but encouraged,
176	to fill out as it will not be submitted to the researchers. The
177	intended purpose of the log is to aid in answering the monthly
178	questionnaire on weekly activity, time in brace, and rest time.
179	8. At 1, 2, and 3 months, a study team member will email the subject's parent the
180	OxAFQ-C, VAS and questionnaire on activity/brace usage. During this time,
181	subjects will also answer questions pertaining to pain medicine use and any
182	adverse outcomes from brace use. A reminder phone call will be made if the

183 184 185 186 187		iv.	questionnaires have not been completed within 5 days. Subjects will not be seen after the visit where consent was obtained, unless an adverse outcome arises requiring an assessment by [name].Planned Duration of Study1. Two-years from COMIRB approval date to allow for adequate enrollment

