iii. Analysis Plan: Demographic and clinical characteristics will be summarized and compared between the two treatment groups using chi-squared and two-sample ttests for categorical and continuous data, respectively. Imbalance between groups will be adjusted for in subsequent statistical analyses. For hypothesis 1, Linear mixed model regression analyses will be used to compare group differences

ii.

319 (Cheetah Brace vs X brace) across the 1, 2 and 3 month visits. We will test the null 320 hypothesis that the difference between groups does not depend on time 321 (group*time interaction). The parameter estimate will be tested using the Wald 322 statistic with Kenward-Roger degrees of freedom and an alpha level of 0.05. 323 Intent-to-treat analyses will be performed for all the primary outcome variables. A 324 per-protocol analysis will also be performed. For the secondary analysis, the other 325 two domains of the OxAFQ-C questionnaire as well as VAS pain scores will be 326 analyzed using separate linear mixed models that iwill also test the group*time 327 interaction. Linear regression models will also be used to compare overall 328 compliance. Logistic regression models will be used to test the null hypothesis of 329 no difference between groups for each of the three brace acceptability metrics 330 (comfort, appearance, and perceived effect on athletic performance).

331

334

335

336

337

338

339

340

341 342

343

344

345

350

332 333

G. Summarize Knowledge to be Gained:

It is common practice to provide heel cups and stretching exercises for patients with Sever's. Because these heel cups cannot be used in barefoot athletes, alternative braces are used. Currently, there are two commonly used braces in barefoot athletes, Cheetah Heel Cups and the The X Brace. No previous study has looked at the effectiveness of these braces. This study would compare these braces in a blinded clinical trial to determine if these braces are effective and if one brace is more effective in decreasing severity of pain in barefoot athletes with Sever's. This study will contribute to the understanding of treatment for barefoot athletes with Sever's disease and will improve patient outcomes by affecting clinical practice. In order to improve quality of life and allow young athletes to remain active, this prospective, randomized treatment study will compare the effectiveness of two braces in decreasing pain severity in barefoot athletes diagnosed with Sever's disease.

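### Baseline OxAFQ-C and VAS are collected before randomization but have no pre-specified place in the mixed models, and an undefined imbalance rule decides which covariates enter

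*Combined protocol and SAP*

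**What the plan says.** - **Baseline data.** Methods (IV.D.iii) step 5: "Subject will complete initial demographics survey, OxAFQ-C, and VAS". Step 6 follows: "Subject will be randomized into either the Cheetah Heel Cup or The X Brace". The order gives a pre-assignment measurement of the primary outcome.
- **Primary model.** The Analysis Plan (IV.F.iii) compares the braces over months 1, 2 and 3 and tests group by time. Baseline is neither a covariate nor a time point, and Table 1 has no baseline column.
- **Covariates.** After chi-squared and t-tests of demographic and clinical characteristics by arm, the plan says only: "Imbalance between groups will be adjusted for in subsequent statistical analyses".
- **Candidate variables.** The list headed "B. Explanatory Variables" (IV.B) runs from age to items such as "Hours per week in a barefoot sport" and brace history. It does not contain the baseline OxAFQ-C or VAS.
- **Blinding.** Step 6 keeps the assignment from the PI and the statistician ("The random assignment will be kept blind to the PI and" the statistician).
- **Remote enrolment.** Under step 1, once signed consent is in, the assigned brace "will be sent in the mail to the family and the associated questionnaires will be" emailed. That sentence gives no order between the baseline questionnaires and the assignment.

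**The concern.** A baseline measurement of the outcome is often its best available predictor, and here it is already collected. The plan gives it no stated use. It could enter only if someone counts it among the clinical characteristics and then judges it imbalanced.

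Differences between randomized arms at baseline are chance. A rule that adjusts for whatever happens to differ therefore lets chance choose the model, and with no threshold, list or form, two analysts following the plan faithfully could fit different primary models. The choice also stays open until data have been compared by arm.

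Two things are at stake: a primary model fixed in advance, and the precision of the brace difference, which matters because Hypothesis 1 is worded as a mean score difference set against 7 points.

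**Working it through.** **Inputs from the documents (IV.F.i and Table 1).** 22 per arm; SD 6; correlation 0.6 between consecutive time points; expected brace differences 67 − 64 = 3, 83 − 82 = 1 and 85 − 78 = 7 at months 1, 2 and 3; alpha 0.05; stated power 0.9.

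**Assumptions not in the documents.** Baseline SD 6; baseline-to-follow-up correlation r, shown as a range; complete data; compound symmetry (CS) or AR(1) at months 1 to 3, since the month 1 to month 3 correlation is not given.

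**1. The plan's own figure.** The Hotelling-Lawley test of group by time has 2 and 41 df. Under CS the noncentrality is (22/2) × Σ(d − mean d)² / [36 × (1 − 0.6)]. The mean of 3, 1 and 7 is 3.667 and the sum of squares is 18.67, so it is 11 × 18.67 / 14.4 = 14.26 and power is 0.913. AR(1) gives 14.00 and 0.908. The stated 0.9 is reproduced.

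**2. Precision at one visit.**
- Unadjusted half-width: t(0.975, 42) × √(2 × 36/22) = 2.018 × 1.809 = 3.65 points.
- Adjusted half-width: t(0.975, 41) × √[(2 × 36/22) × (1 − r²) × (1 + 1/40)]. The last factor is the average price of estimating the baseline slope.

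| r | Adjusted half-width | Net variance change, (1 − r²) × 1.025 − 1 |
|---|---|---|
| 0.1 | 3.68 | +1.5% |
| 0.2 | 3.62 | −1.6% |
| 0.3 | 3.53 | −6.7% |
| 0.4 | 3.39 | −13.9% |
| 0.5 | 3.20 | −23.1% |
| 0.6 | 2.96 | −34.4% |

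The two half-widths are equal at r of about 0.16. If AR(1) with 0.6 is carried back to baseline, r is 0.6, 0.36 and 0.216 at months 1, 2 and 3, and the half-widths are 2.96, 3.45 and 3.61. At month 3, where Table 1 shows the 7-point difference, the gain is then only 3.65 to 3.61.

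**3. Effect on the planned group-by-time test.** With baseline and its interaction with visit (2 and 40 df, noncentrality divided by 1.025):
- CS throughout: 0.913 becomes 0.906.
- AR(1) throughout: 0.908 becomes 0.905.
- CS at follow-up with baseline correlations falling 0.6, 0.4, 0.2: 0.913 becomes 0.933.

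A baseline equally correlated with every visit cancels from the contrasts between visits, so it cannot help this test. One whose correlation decays can help a little.

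**4. How often chance triggers the rule.** Suppose imbalance meant p < 0.05. The IV.B list has 11 usable candidates: age, gender, ethnicity, weight, height, BMI, athletic participation, primary sport, weekly hours, previous diagnosis and previous brace. If independent, the chance of at least one flag is 1 − 0.95¹¹ = 0.43. Weight, height and BMI are linked, and previous brace is nested under previous diagnosis; with 6 effective variables it is 1 − 0.95⁶ = 0.265, about 27%.

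**5. What the present rule would recover.** Even if baseline OxAFQ-C counts as a candidate, at a 0.05 threshold it enters in about 5% of trials. In simulation (40,000 null trials, correlation 0.6) the month-3 half-width is then 3.63 under CS, against 2.96 if always adjusted, and 3.66 under AR(1), against 3.61.

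**The case against.** **The precision gain concerns something the plan does not test.** The only planned primary test is group by time, no interval at each visit is specified, and Hypothesis 1 names no visit. This stands in part. Reading the 7-point criterion as a difference at a visit is an interpretation, though a 7-point claim needs an estimated difference of some kind.

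**The size of the gain is not known.** This stands. Neither r nor the baseline SD is in the documents, and the range runs from slightly worse to a 34% fall in variance.

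**Blinding limits misuse.** It does, but it does not close the choice, because a comparison of coded arms still shows the p-value of each candidate model. The exposure for the planned test is small: always keeping the smaller p-value, with or without baseline, gives simulated null rejection of about 0.055 to 0.063.

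A reader might also infer more than the documents support:
- *That the unadjusted comparison is biased, or that testing then adjusting inflates false positives.* Randomization makes the first unbiased. A fixed test-then-adjust rule kept null rejection of group by time at or near 0.05 in simulation.
- *That baseline adjustment never helps the group-by-time test.* Step 3 of the working shows that this depends on the correlation structure.
- *That the baseline scores are shut out altogether.* They could be read as clinical characteristics, so the fault is that their place is not pre-specified.
- *That remote families give baseline scores after assignment.* Steps 5 to 7 are numbered for all subjects, ending with "Subject will receive their assigned brace in the mail following their consent visit". Step 1 states no exception; it only leaves the order unconfirmed.

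**Conclusion.** The point holds as a recommendation that should be adopted, not as a flaw that invalidates the trial. The plan collects the baseline outcome, gives it no pre-specified role, and leaves all covariates to an undefined rule driven by chance. That part rests on the text alone.

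The size of the precision loss rests on the assumed r. Per visit, adjustment would change the half-width from 3.65 to between 3.68 (r 0.1) and 2.96 (r 0.6), and at month 3 under AR(1) only to 3.61. Group-by-time power stays near 0.91, or reaches about 0.93 if the baseline correlation decays while follow-up is CS. The 27% to 43% chance of a spurious flag assumes a 0.05 threshold. Confidence is medium because r is unknown.

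**What to change.** Replace the imbalance sentence in IV.F.iii with:

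*Each mixed model for the OxAFQ-C domains and VAS includes the baseline value of the same score and its interaction with visit, whatever the observed balance. Baseline characteristics are described by arm without significance tests. Any further covariate is named before any data are examined by arm. The adjusted brace difference is reported with its 95% CI at each visit.*

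Add two lines. The step 5 questionnaires are completed before the step 6 assignment, for remote families too. A missing baseline score is replaced by the mean of that score pooled over both arms. A rule keyed to when the brace arrived is best avoided, because the documents do not describe recording that date.

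**Cost.** This is SAP wording and one sequencing line; step 5 already collects the scores. It uses three model degrees of freedom. In the cases where group-by-time power falls, it falls by less than 0.01 (0.913 to 0.906; 0.908 to 0.905). If r is only 0.1, the half-width is 0.03 points wider (3.68 against 3.65).

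**Limit.** The change does not reconcile the 7-point criterion in Hypothesis 1 with the group-by-time test; that needs its own correction.

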COMIRB Protocol

COLORADO MULTIPLE INSTITUTIONAL REVIEW BOARD [name] [contact] [contact]

- 1
- 2 Protocol #: 17-0611
- 3 Project Title: Comparison of braces for treatment of Sever's disease
- 4 Principal Investigator: [name]
- 5 **Version Date:** 03/25/2020
- 6

7 I. Hypotheses and Specific Aims:

8 Primary Aim: To compare two types of braces: The X Brace (The X Brace, Grand Rapids, MI) and 9 Cheetah Heel Cups (Tuli's[®], Medi-Dyne, Colleyville, TX), in pain reduction for barefoot athletes (e.g. 10 karate, gymnasts, dancers) diagnosed with Sever's disease (calcaneal apophysitis)

- 12 Hypothesis 1 - The Cheetah Heel Cup will be significantly more effective than The X Brace 13 in reducing pain for barefoot athletes diagnosed with Sever's disease, demonstrated by a 14 mean score difference greater than the minimal detectable difference (7 points) on the 15 OxAFQ-C in the physical domain.
- 16

11

17 II. Background and Significance:

18 Sever's disease is an osteochondrosis of the calcaneal apophysis due to frequent repetitive foot 19 impact and repeated traction from the Achilles tendon, which attaches to the apophysis.¹ Though 20 there remains uncertainty about the exact pathomechanics of this ailment, it is generally 21 considered an overuse injury affecting active skeletally-immature children aged 8-14 years.² Identified risk factors include high levels of athletic activity,³ increased BMI,^{4,5} and anthropometric 22 23 differences compared to a normative peer group including increased weight, height, ankle range of 24 motion, waist circumference, and foot posture index.⁵ A recent, large cross-sectional study 25 examining visits to primary care practices reported an incidence of 3.7 per 1,000 patients ages 6-17 26 with a median age of 10 years for girls and 12 years for boys.⁶ One systematic review reports that 27 Sever's accounts for 2%-16% of musculoskeletal complaints in children.⁷ This condition, which 28 presents as heel pain with physical activity, is one of the most common pathological entities among 29 this age group and a serious concern for growing athletes.⁶

30

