- 283 i. Sample Size: We will use a linear mixed model to test the null hypothesis that the 284 difference in OxAFQ-C physical domain scores between the The X Brace and 285 Cheetah Heel Cups does not depend on time (group*time interaction). Means for 286 treatment group at each time point were estimated based on a related RCT by James et al. ¹³. The common standard deviation for all OxAFQ-C physical domain 287 scores was assumed to be 6 and the correlation between time consecutive points 288 289 was conservatively assumed to be 0.6 based on this previous RCT. We intend to 290 use a one-to-one block randomization scheme to ensure equal allocation of 291 patients to each treatment group. Assuming a Type 1 error rate of 0.05, a sample 292 size of 44 participants total, 22 in each group, will provide 0.9 power to reject the 293 null hypothesis of no group*time interaction based on the Hotelling-Lawley test 294 statistic with an alpha level of 0.05. Assuming there is no missing data, no time 295 varying covariates, and the repeated measures are consistently collected (general 296 linear mixed model reversibility criteria is met), the Hotelling-Lawley trace statistic 297 is equivalent to the statistical test, the Wald statistic with Kenward-Roger degrees of freedom, described in the data analysis plan.²⁰. With an expected 30% loss to 298 299 follow up, we will inflate the sample size to account for attrition, for a total 300 enrollment goal of 58. The clinic treats 10 barefoot athletes with a clinical 301 diagnosis of Sever's Disease who meet the eligibility criteria for this study each 302 month. We expect a consent rate of approximately 50%. At an effective enrollment 303 rate of 5 patients per month, we will reach the enrollment goal of 58 participants 304 within 12 months. All samples size calculations were performed with GLIMMPSE, 305 an internet based open source software program capable of computing power and 306 sample size for multi-level and longitudinal research designs²¹
- 307 308
- 309

310 311 Table 1. Expected OxAFQ-C physical domain scores based on data from James et al^{13}

Treatment	1 month	2 months	3 months
Cheetah Heel Cups	67 (±6)	83 (±6)	85 (±6)
The X Brace	64 (±6)	82 (±6)	78 (±6)

312 313

314

315

316

317

318

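### The primary test asks whether the brace difference changes between months 1 and 3, not whether Cheetah is better, so it does not test Hypothesis 1

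*Combined protocol and SAP*

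**What the plan says.** Section I states the hypothesis as one of level and direction: "The Cheetah Heel Cup will be significantly more effective than The X Brace", to be shown by a "mean score difference greater than the minimal detectable difference (7 points) on the" physical domain of the OxAFQ-C. It names no visit.

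For this hypothesis, Section IV.F.iii fits a linear mixed model "across the 1, 2 and 3 month visits". The one null it states is the "hypothesis that the difference between groups does not depend on time", tested by a Wald statistic with Kenward-Roger degrees of freedom at 0.05. Section IV.F.i bases the sample size on the same interaction: 44 participants, 22 per group, for 0.9 power.

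The OxAFQ-C is also collected before randomization (Section IV.D.iii, item 5: "Subject will complete initial demographics survey, OxAFQ-C, and VAS"). Baseline is not among the model's visits and has no column in Table 1. No group main effect, single-visit contrast, average over visits or rule on direction is specified. The other two OxAFQ-C domains and the VAS are to be tested by the same interaction.

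**The concern.** A group-by-time interaction over three follow-up visits asks whether the gap between braces widens or narrows from month 1 to month 3. It does not ask how large the gap is or which brace is ahead. If Cheetah were better by the same amount at every visit, the null would be true.

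The sign is also lost. Differences of +7, +3, 0 and of -7, -3, 0 give the same p-value, and adding any constant to all three differences changes nothing.

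Followed as written, the trial could observe a large sustained benefit and have to report a non-significant primary result. It could also report significance when Cheetah is no better or is worse. The 0.9 power would then belong to a question the hypothesis does not ask.

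**Working it through.** **Inputs (Section IV.F.i and Table 1).** SD 6 at every visit; correlation 0.6 between consecutive visits; n = 22 per arm; alpha 0.05. Expected means at months 1, 2, 3 are 67, 83, 85 (Cheetah) and 64, 82, 78 (X Brace), so the differences are d = (3, 1, 7). The correlation between months 1 and 3 is not given. I used 0.6 (compound symmetry, CS) and 0.36 (AR(1)) as the range.

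**Interaction test.** With two groups and three visits, the Hotelling-Lawley test has 2 and 2n - 3 = 41 degrees of freedom. Its noncentrality is

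λ = (n/2) · (Cd)′(CΣC′)⁻¹(Cd),

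where C takes month 1 minus month 2 and month 2 minus month 3.

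**The plan's own figure.** For d = (3, 1, 7), Cd = (2, -6).
- CS: CΣC′ has 28.8 on the diagonal and -14.4 off it, with determinant 622.08. λ = 11 × (28.8×4 - 2×14.4×12 + 28.8×36)/622.08 = 11 × 806.4/622.08 = 14.26. Power is 0.913.
- AR(1): the off-diagonal is -5.76 and the determinant 796.26. λ = 11 × (28.8×40 - 2×5.76×12)/796.26 = 11 × 1013.76/796.26 = 14.00. Power is 0.908.

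The stated 0.9 reproduces, and 22 is the smallest number per arm that reaches it.

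**A constant advantage.** For d = (c, c, c), Cd = (0, 0) and λ = 0 for every c, so the rejection rate is 0.05. Simulation (20,000 trials) at c = 7 gave 0.049 (CS) and 0.050 (AR(1)).

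**Level contrasts.** At month 3 the standard error is 6 × √(2/22) = 1.81, so 7 points gives 7/1.81 = 3.87 on 42 df and power 0.966. The contrast averaged over visits uses the variance of the mean of three scores, 26.4 (CS) or 24.48 (AR(1)).

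Power or rejection rate at 22 per arm, two-sided 0.05, against zero difference (CS / AR(1)):

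| True difference, months 1, 2, 3 | Interaction (planned) | Month 3 | Average of visits |
|---|---|---|---|
| 3, 1, 7 (Table 1) | 0.91 / 0.91 | 0.97 | 0.64 / 0.67 |
| 7, 7, 7 | 0.05 / 0.05 | 0.97 | 0.99 / 1.00 |
| 5, 6, 7 | 0.17 / 0.12 | 0.97 | 0.97 / 0.98 |
| 3, 5, 7 | 0.56 / 0.37 | 0.97 | 0.88 / 0.91 |
| -4, 0, +4 | 0.99 / 0.93 | 0.58 | 0.05 / 0.05 |
| -3, -1, -7 | 0.91 / 0.91 | 0.97 (favouring X Brace) | 0.64 / 0.67 (favouring X Brace) |

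**Direction.** The last row, with X Brace ahead at every visit, has the same interaction power as the planning case. In the simulated trials that were significant under it, the observed average favoured Cheetah about 1% of the time.

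**The case against.** **Baseline may have been meant as a time level.** The aim speaks of reducing pain, and baseline scores are collected. With baseline as a fourth level, no baseline difference, and the same SD and correlation assumed, a constant 7-point advantage would be detected with 0.99 (CS) / 0.96 (AR(1)) power. But both analysis sections list months 1 to 3 only. The stated power also fits three levels (0.91) better than four, where Table 1 would give 0.97 / 0.95. A four-level test would still not show which brace scores higher.

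**Month 3 is a choice.** This stands. Hypothesis 1 names no visit, and the average over visits would have only 0.64 / 0.67 power under Table 1, less than the interaction. Month 3 is supported because Table 1 places the 7-point difference there. With differences of -4, 0, +4 a month-3 test rejects 58% of the time, which is proper only if month 3 is the declared target.

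**A test against zero does not show a difference above 7.** This stands too. If the true difference is exactly 7, a test against 7 rejects only at its alpha level. With 22 per arm, 0.90 power to show more than 7 (two-sided 0.05) needs a true difference of about 13, since (13 - 7)/1.81 = 3.32.

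**A two-sided month-3 test also ignores sign in its p-value.** True, but its estimate says which brace is ahead. An interaction estimate does not.

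**Exactly parallel profiles are the extreme case.** They are, but the steadily widening patterns 5, 6, 7 and 3, 5, 7 also leave power far below 0.9.

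**Conclusion.** The concern holds. The only test planned for the only hypothesis, and the one that sets the sample size, does not address that hypothesis. A constant Cheetah advantage is missed 95% of the time whatever its size. A steadily widening one reaching 7 points at month 3 has power between 0.12 and 0.56 in the patterns examined. A significant result need not favour Cheetah. The 0.9 is correctly calculated but depends on the 3, 1, 7 pattern in Table 1. The secondary OxAFQ-C domains and the VAS have the same defect.

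The power figures assume complete data at 22 per arm, SD 6, and a month 1 to month 3 correlation between 0.36 and 0.6. The 5% rejection rate under a constant difference follows from the definition of the test and does not depend on the SD or correlation.

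**What to change.** - **Section IV.F.iii:** make the primary test the Cheetah minus X Brace difference in OxAFQ-C physical score at month 3. Estimate it from the same linear mixed model (group, visit, group-by-visit) with Kenward-Roger degrees of freedom and two-sided alpha 0.05, and report a confidence interval. Keep the month-1, month-2 and averaged differences and the interaction test as supportive.
- **Secondary OxAFQ-C domains and VAS:** make the same change.
- **Section IV.F.i:** restate the power as about 0.97 for a 7-point difference at month 3 with SD 6 and 22 per arm.
- **Section I:** name month 3. Say whether 7 points is a benchmark for judging the estimate and its interval or a value to be formally exceeded; the 0.97 applies only to the first.

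The cost is protocol and analysis-plan wording: the model, data and sample size do not change. Month 3 must be named as the primary visit, and a difference in profile shape alone would no longer count as the primary result. The documents do not give enrolment status, so the change should be dated and made before anyone sees outcome data by group.
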